7.2.2. Exclusion Criteria

Patients meeting any of the following criteria will not be included in the study:

- e) Patients with any of the following diagnoses prior to the use of the treatments of interest or index date:
 - Valvular heart disease or valve replacement – ICD-10 codes: I05, I06, I07, I08, I09, I22, I34, I35, I36, I37, I38, I39, I700, I702-I709; Q22, Q23, Q25, T82,Z95.
 - Pregnancy during the study period. ICD-10 O00-O9A
 - Diagnosis of venous thromboembolism (VTE) – ICD-10 codes: I26, I80 - I82;
- f) Individuals with a transitory diagnosis of NVAF prior to the use of the treatments of interest or index date;
- g) Exposure to more than one OAC on or after the index date, during the follow-up period.
- h) NOAC doses different from those recommended by the manufacturing laboratories.

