Persistence	Clinical outcome	Claim databases	Yes, No
OAC treatment	Treatment	Claim databases	Warfarin, apixaban, rivaroxaban, dabigatran
Diagnosis at index date	Treatment	Claim databases	Diagnosis AF based on ICD-10
Date of OAC prescription	Treatment	Claim databases	Date reported dd/mm/yy
Dosage of the initial OAC treatment	Treatment	Claim databases	Mg per dose
Initial frequency of OAC treatment	Treatment	Claim databases	Number of doses at initial OAC treatment
OAC escalation	Treatment	Claim databases	Yes, No
Type of OAC escalation	Treatment	Claim databases	Dose increase or dose decrease
Time to OAC escalation	Treatment	Claim databases	Date reported dd/mm/yy
CCI			

Variable	Role	Data source (s)	Operational definition
CCI			
INR testing monthly in patients with warfarin	Treatment	Medical record	INR reported in the medical record per month
Switch to another OAC treatment:	Treatment	Claim databases	Yes, No
Time to Switch to another OAC treatment	Treatment	Claim databases	Date reported dd/mm/yy
Causa de cambio	Treatment	Medical record	Adverse events, effectiveness, adherence, patient preference, administrative problems, not reported, others
Concomitant therapies by OAC prescription	Treatment	Medical record	NSAIDs, Angiotensin-converting-enzyme (ACE) inhibitors, Amiodarone, Beta-blockers, Angiotensin II receptor blockers (ARBs), Aspirin, Clopidogrel, Digoxin, Diuretics, calcium blockers, statins, proton pump inhibitor, selective H2 antagonists, antidiabetics, insulin, serotonin reuptake inhibitors
Previously exposed to warfarin	Treatment	Claim databases	Yes, No

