7.3.1. Definition of outcome variables

- **OAC escalation:** The dose escalation of the OAC dose will be considered as a dose frequency according to the index dose, as well as the follow-up doses. The proportion of patients experiencing "dose increase", "dose decrease" or "no change" during follow-up with respect to the index dose will be measured, and the time to dose increase or decrease will be calculated.

C
C
I

C
C
I

- **Switch of treatment:** A switch among anticoagulants will be defined as a prescription filled for non-index anticoagulants within +/- 30 days after the date of discontinuation.
- **Persistence:** Persistence will be defined as the time under OAC therapy, calculated as the time in days from the index date to the date of discontinuation or change to treatment. As previously stated, discontinuation will be defined as a change of treatment, that is, to another OAC, or when there is no evidence of a prescription for 60 days from the last supply delivered, whichever comes first.

Therefore, if a patient does not receive his next prescription for the OAC therapy within 60 days after the end of the previous prescription, it will be considered that he discontinued therapy, and the date of the last prescription will be considered as the final date of persistence.

Persistence with OAC therapy will be considered during the period of individual patient follow-up. Patients will be censored at the end of their follow-up period.

- **Major bleeding:** Patients presenting any of the following diagnoses during the follow-up period:

ICD-10	Description
I60	Subarachnoid haemorrhage
I61	Intracerebral haemorrhage
I62	Other nontraumatic intracranial haemorrhage
I690	Sequelae of subarachnoid haemorrhage
I691	Sequelae of intracerebral haemorrhage
I692	Sequelae of other nontraumatic intracranial haemorrhage
S064	Epidural haemorrhage
S065	Traumatic subdural haemorrhage
S066	Traumatic subarachnoid haemorrhage
I850	Oesophageal varices with bleeding
K250	Acute with haemorrhage

Apixaban

B0661148- NON-INTERVENTIONAL STUDY PROTOCOL

Final, 10 October 2019

ICD-10	Description
K252	Acute with both haemorrhage and perforation
K254	Chronic or unspecified with haemorrhage
K256	Chronic or unspecified with both haemorrhage and perforation
K260	Acute with haemorrhage
K262	Acute with both haemorrhage and perforation
K264	Chronic or unspecified with haemorrhage
K266	Chronic or unspecified with both haemorrhage and perforation
K270	Acute with haemorrhage

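### The switch definition in 7.3.1 is circular and its dates conflict, so one claims record can be a switch or not depending on which sentence is applied

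*Combined protocol and SAP*

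**What the plan says.** All the rules are in section 7.3.1 of the protocol.

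- **Switch:** "A switch among anticoagulants will be defined as a prescription filled for non-index anticoagulants within +/- 30 days after the date of discontinuation".
- **Persistence** is "calculated as the time in days from the index date to the date of discontinuation or change to treatment".
- **Discontinuation, change route:** "discontinuation will be defined as a change of treatment, that is, to another OAC".
- **Discontinuation, gap route, first statement:** "no evidence of a prescription for 60 days from the last supply delivered, whichever comes first".
- **Discontinuation, gap route, second statement:** the patient "does not receive his next prescription for the OAC therapy within 60 days after the end of the previous prescription".
- **Date of a gap-based stop:** "the date of the last prescription will be considered as the final date of persistence".

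Table 1 (section 7.3) records switching as yes/no from claims, its cause, and "Time to Switch to another OAC treatment". Under 7.1, follow-up ends at a switch or at discontinuation, among other events. Under 7.7, change of treatment is a censoring event for the clinical outcomes, and time to change is to be estimated in patients free of those outcomes. Exclusion (g) in 7.2.2 removes patients with "Exposure to more than one OAC on or after the index date, during the follow-up period".

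Some text directly above the switch bullet is blacked out. The persistence bullet refers back to an earlier statement of discontinuation that is not visible in 7.3.1.

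**The concern.** A switch is located by the date of discontinuation, and one of the two kinds of discontinuation is a change of drug. The definition therefore refers to itself. Under the change route the new fill lies zero days from discontinuation, and the 30-day window excludes nobody. The window has work to do only when discontinuation comes from a gap. That stop is dated to the last fill rather than to the end of supply, so the days for which the patient still holds drug use up the window.

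Two further points are open. The gap has two starting points that differ by the full length of the supply. The window combines a two-sided sign with a word that means one side only, so the status of a fill shortly before the stop date is unclear.

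At stake are the proportion switching, the time to switch and the division of patients into switched and stopped. These belong to the treatment patterns named as a primary objective. Because follow-up ends at the same dates, person-time and captured events in the exploratory outcome analyses depend on them too.

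**Working it through.** The plan gives no figure to reproduce. The check applies the date rules to claims records.

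**Inputs.** The 30-day window, the 60-day gap, the last-prescription dating and the change route come from 7.3.1. Days' supply S is an assumption (28, 30, 60 or 90), because the documents give none.

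**Step 1: one record.** Index fills on days 0, 30 and 60 with 30-day supplies; supply ends on day 60 + 30 = 90; another anticoagulant is filled on day 95.

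- Last-fill dating: discontinuation is day 60. The two-sided window is days 30 to 90, and the one-sided window is days 60 to 90. Day 95 lies outside both: not a switch.
- Change route: the gap rule would trigger on day 60 + 60 = 120 (from delivery) or day 90 + 60 = 150 (from end of supply). Day 95 precedes both, so discontinuation is day 95 and the distance is 0: a switch.
- The two stop dates differ by 95 − 60 = 35 days of follow-up.

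**Step 2: general case.** Set day 0 at the last index fill. Let g be the days from end of supply to the first fill of another anticoagulant, so that fill is on day t = S + g. It counts as a switch if |t − D| ≤ 30, where D is the discontinuation date.

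- Reading A (last-fill dating, change route not applied): D = 0, so the condition is S + g ≤ 30.
- Reading B (change route, gap from end of supply): D = t whenever g ≤ 60; otherwise D = 0.
- Reading C (change route, gap from delivery): D = t whenever S + g ≤ 60; otherwise D = 0.

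Values of g (0 or more) that count as a switch:

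| Assumed supply S | Reading A | Reading B | Reading C |
|---|---|---|---|
| 28 days | 0 to 2 | 0 to 60 | 0 to 32 |
| 30 days | 0 only | 0 to 60 | 0 to 30 |
| 60 days | none | 0 to 60 | 0 only |
| 90 days | none | 0 to 60 | none |

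For comparison, a 30-day window starting at the end of supply would count g = 0 to 30 for every S. No reading gives that throughout; reading C gives it only at S = 30.

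**Step 3: exclusion (g).** Read literally, it removes anyone who receives a second anticoagulant during follow-up. The number of switches would then be zero under every reading, and the switch rows of Table 1 would be empty.

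**The case against.** A reader might infer that a patient who finishes the supply and then starts another drug is simply not counted as a switch. The visible text does not support that flat statement. Discontinuation is the earlier of a change and a gap, and last-prescription dating is written for the patient who has no next prescription within 60 days. On the natural reading of the first-to-occur rule, the day-95 change precedes either gap trigger and counts. This objection stands, and it limits the point to inconsistency. It does not remove it: the rule does not say whether trigger dates or assigned dates are compared, and a gap stop back-dated to day 60 would come before day 95.

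A reader might also want a percentage of lost switches. For a 30-day supply and new fills spread evenly over −15 to +15, −10 to +30 or −10 to +60 days around end of supply, reading A misses 15/30 = 50%, 30/40 = 75% and 60/70 = 86%. Reading B misses none. Reading C misses 0%, 0% and 30/70 = 43%. The answer depends on the reading and on assumed timing, so none of these is an estimate for this study.

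Two more objections carry weight. The blacked-out text may hold a definition and date of discontinuation, and taking the end of persistence as the date of discontinuation is an inference, though the persistence sentence supports it. The time-to-change analysis is also listed as exploratory, and 7.7 plans no treatment comparison. Even so, the visible sentences conflict with one another, and switching is a recorded treatment-pattern variable whatever the status of the Kaplan-Meier analysis.

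**Conclusion.** The visible switch definition is circular and internally inconsistent, and two programmers working from it could classify the same patient in opposite ways. With last-fill dating, or with a gap counted from delivery and supplies of about 60 days or more, a patient who starts another drug soon after finishing the supply is not a switch (the exact last day of supply can be an exception, as the table shows). With the change route and a gap counted from end of supply, every such patient within 60 days is a switch and the 30-day window never binds.

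The size is a range of rules, not a bias estimate: the longest delay that counts runs from none to 60 days, and in the worked record the end of follow-up moves by 35 days. Both rest on assumed supply lengths. The documents do not show that most switchers are lost, nor what the 30-day limit was meant to exclude. The point should be settled before the claims are coded. It does not put the study design in doubt.

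**What to change.** Replace the switch sentence in 7.3.1 with a rule anchored on supply, for example: *Switch = first fill of a non-index OAC after the index date and no later than N days after the end of the days' supply of the most recent index-OAC fill; switch date = date of that fill.*

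- Set N = 60 to match a single 60-day gap counted from end of supply, and delete the count from delivery.
- Delete the +/- sign and the reference to the date of discontinuation, which removes the circularity.
- State one discontinuation date for each route.
- Do not require the absence of later index-drug fills. Follow-up ends at the switch, so a later return should not undo it.
- Report the switch proportion with N = 30 as a sensitivity check.
- Reconcile exclusion (g) in 7.2.2 with the switch variables in Table 1, since the new rule has no effect if switchers are removed first.

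In the worked record the rule gives a switch on day 95 under both settings (limits: day 90 + 60 = 150 and day 90 + 30 = 120).

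The cost is a short text edit, a few lines of code on claims already held, and one extra table. The rule needs days' supply for each fill. No visible row of Table 1 lists it, although some rows are blacked out; the existing count from the end of the previous prescription needs it as well.

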6. RESEARCH QUESTION AND OBJECTIVES

Primary Objectives

- To assess demographic and clinical characteristics of NVAF patients treated with oral anticoagulants (OACs) in Colombia.
- To describe treatment patterns (eg. OAC usage, dose, concomitant medications, persistence)

Exploratory Objectives

- To descriptively assess the time to clinical events (Effectiveness and Safety Outcomes) among patients persistent on OAC therapy.

Effectiveness outcomes: First Stroke/ Systemic Embolism; CCI

Safety outcomes: Major bleeding, CCI

[figure not shown]

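### Persistence for refill-gap discontinuers ends on the last fill date, so the last supply is not counted and a single-fill patient gets 0 days; the start of the 60-day gap also needs one wording.

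*Combined protocol and SAP*

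**What the plan says.** Section 7.3.1 gives the concept first: "Persistence will be defined as the time under OAC therapy". The same sentence then gives the formula, under which persistence is "calculated as the time in days from the index date to the date of discontinuation or change to treatment". Section 7.1 sets the index date at the first prescription of an oral anticoagulant, and inclusion criterion (b) in Section 7.2.1 takes the start as delivery of the drug by the insurer.

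Discontinuation is a change to another anticoagulant or a refill gap. The gap is described twice:

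- as arising "when there is no evidence of a prescription for 60 days from the last supply delivered, whichever comes first";
- in the next paragraph, as having no new prescription "within 60 days after the end of the previous prescription".

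For these gap patients, "the date of the last prescription will be considered as the final date of persistence". The others are handled differently: a switcher ends at the change of treatment, and for the rest "Patients will be censored at the end of their follow-up period".

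A switch is a fill of a non-index anticoagulant "within +/- 30 days after the date of discontinuation". The second primary objective in Section 6 is "To describe treatment patterns (eg. OAC usage, dose, concomitant medications, persistence").

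**The concern.** The end date does not measure the stated construct. Time under therapy should include the days covered by the last supply, but the rule stops the clock on the day that supply is handed over. The sentence that sets this date also speaks of the end of the previous prescription, so the protocol itself separates the date of a prescription from its end.

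The shortfall falls on refill-gap discontinuers only, so it moves persistence time in one direction, downward. If the same date serves as the discontinuation date elsewhere, two more things move: the switch window, and the end of follow-up for stroke/systemic embolism and bleeding, because Section 7.1 stops follow-up at discontinuation.

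The second point is smaller. Read literally, the two gap wordings differ by one full supply.

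**Working it through.** **Inputs.** From Sections 7.1 and 7.3.1: start at the first prescription, end at the last prescription for gap patients, a 60-day gap, and a switch window of 30 days either side. Not given in the visible text: days' supply per fill, S. I assume 30, 60 and 90. The protocol states no persistence figure, so there is none to reproduce.

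**Step 1: date arithmetic.** With k on-time fills, the rule gives (k-1) x S days and the supply covers k x S. The loss is S days, or 1/k of the supplied time.

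- k = 1: 0 days instead of S (100% lost).
- k = 2, S = 30: 30 instead of 60 days (50% lost).
- k = 6, S = 30: 150 instead of 180 days (16.7% lost).
- k = 12, S = 30: 330 instead of 360 days (8.3% lost).

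**Step 2: gap start.** Counted from delivery, the cut-off is day 60 after the last fill. Counted from the end of supply, it is day S + 60, that is day 90, 120 or 150. With S = 90, the count from delivery, taken literally, discontinues a patient who refills on time at day 90.

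**Step 3: switch window, in days after the last fill.** Anchored at the last fill it is -30 to 30. Anchored at the end of supply it is S - 30 to S + 30:

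- S = 30: 0 to 60 (overlap on days 0 to 30);
- S = 60: 30 to 90 (one shared day);
- S = 90: 60 to 120 (no overlap).

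**Step 4: effect on one-year persistence.** I simulated 400,000 patients per setting.

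- The number of fills n is geometric, with continuation per fill q^(1/12), q^(1/6) or q^(1/4) for S = 30, 60 or 90. Supply-based one-year persistence is then q, set at 50% or 70%.
- Refills are on time and the last supply is assumed taken.
- Administrative follow-up is uniform from 365 days (entry 30 June 2018) to 2,371 days (entry 1 January 2013), both ending 30 June 2019.
- Other exits are exponential at 0, 10 or 30% a year and are censored.
- A stop is detected only if n x S + 60 lies within follow-up. It is then timed at n x S (end of supply) or (n-1) x S (plan).

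Without any censoring the plan's value is q^(13/12), q^(7/6) or q^(5/4): 47.2, 44.5 and 42.0% for q = 50%, and 68.0, 66.0 and 64.0% for q = 70%.

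Kaplan-Meier persistence at day 365 (%), end of supply vs plan:

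| Assumed truth | Other exits per year | S = 30 | S = 60 | S = 90 |
|---|---|---|---|---|
| 50 | 0% | 50.1 vs 47.4 | 50.2 vs 45.1 | 50.3 vs 42.8 |
| 50 | 10% | 50.8 vs 48.5 | 50.7 vs 46.3 | 51.0 vs 44.8 |
| 50 | 30% | 52.2 vs 50.7 | 52.4 vs 49.6 | 52.5 vs 48.9 |
| 70 | 0% | 70.1 vs 68.1 | 70.2 vs 66.4 | 70.2 vs 64.7 |
| 70 | 10% | 70.5 vs 68.8 | 70.6 vs 67.4 | 70.5 vs 65.7 |
| 70 | 30% | 71.6 vs 70.5 | 71.6 vs 69.5 | 71.7 vs 68.9 |

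The rules differ by 1.1 to 7.4 points (from unrounded values). Single-fill discontinuers recorded with 0 days are 2.7 to 15.9% of patients. Repeat runs agree to within a few tenths of a point.

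**Step 5: why both estimates rise with exits.** A stop whose 60-day gap is cut off by an exit is censored as still on treatment. If patients without a completed gap are censored 60 days earlier, the end-of-supply rule gives 49.9 to 50.1% and 69.9 to 70.1% in all settings. The last-fill rule gives 42.6 to 48.5% and 64.5 to 69.0%.

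**The case against.** The strongest reply is that both end dates are conventions with opposite errors. My assumed truth treats the last supply as taken, yet Section 7.9 says that a prescription does not show intake. If stops are instead spread evenly over the last supply and the curve is read mid-supply, the errors without exits are nearly equal: for 90-day supplies, 59.4% (end of supply) and 50.3% (plan) around a truth of 54.7%. With exits the planned rule was then closer in all 12 settings. Read at day 365, that same model favoured the end of supply in 11 of 18. In my own table the planned rule is closer in all 6 settings with 30% exits. This stands: the difference between the rules is firm, but which is nearer to true intake depends on assumptions. It does not make the written rule fit the written definition, and part of the planned rule's apparent accuracy comes from two errors that offset each other.

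Other limits also stand.

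- Table 1 records persistence as Yes/No. Over the whole follow-up that does not change; time in days and persistence at a fixed time do. One-year persistence is my illustration, not a named output.
- The visible text does not say that the final date of persistence is the discontinuation date used for switching, so that consequence is conditional. Exclusion (g) in Section 7.2.2, on exposure to more than one anticoagulant, may also remove many switchers.
- Text ahead of the switch and persistence items is blacked out, and the persistence paragraph refers back to an earlier statement. A hidden definition may settle the gap start. It would not alter the visible end-date sentence.
- The visible rows of Table 1 list no days' supply.

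**Conclusion.** The concern holds. As written, the end date for refill-gap discontinuers leaves out the whole last supply and gives single-fill patients 0 days, on a measure named in a primary objective. This part is date arithmetic and needs no outside figure.

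The size rests on assumptions: supplies of 30, 60 or 90 days, on-time refills and the simple stopping model above. Under these, the loss per affected patient is up to one supply (an upper bound, since intake is unknown), and one-year persistence shifts by 1.1 to 7.4 points. That range is a difference between rules, not an error against truth in every setting.

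Patients censored at the end of follow-up are unaffected, and Section 7.7 plans no treatment comparison, so the descriptive level is at stake, not a contrast. The two gap wordings are text to reconcile rather than two established rules. The change should be made before analysis.

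**What to change.** In Section 7.3.1:

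1. For refill-gap discontinuers, end persistence at the last dispensing date plus days' supply, cut at switch, death, disenrolment or end of follow-up.
2. Start the 60-day gap at the end of supply in both sentences, as the second one already does.
3. State that this same date anchors the 30-day switch window.
4. Add two sensitivity analyses: the last-fill end date, and censoring patients without a completed gap 60 days before their last observed day.

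The cost is a wording change and one derived date. Days' supply must be derived for each fill from the claims, but the rule based on the end of the previous prescription already needs it. The drawback is that the new date assumes the last supply was taken, which is why the last-fill date should stay as a sensitivity analysis.

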7. RESEARCH METHODS

7.1. Study Design

Observational, descriptive study of a retrospective cohort of adult patients diagnosed with NVAF in selected Health Maintenance Organization (HMO) of Colombia. These patients will be identified from the drug claim database, whose index date of the study will be the first prescription with any of the oral anticoagulants, that is, they are patients with NVAF for the first time starting a therapy with any of the NOACs between January 1, 2013 and June 30, 2018 and follow up period will be among January 2013 to July 2019, to ensure that the last patients can provide follow-up for one year. Patients will be required to have an NVAF diagnosis before or on the index date and health plan for 6 months pre-index date (baseline period).

Following, it will be verified that the patients meet the inclusion and exclusion criteria of the study. Once patients are selected and with the index date of each patient, they will be followed-up until discontinuation, switch of treatment, death or first event of stroke/ systemic embolism, major bleeding event, death or end of follow-up. Patients who are lost to follow-up, change of HMO and do not have access to the medical record will be considered as missing (Figure 1).

Figure 1. Study Design

[figure not shown]
The information will be analyzed in two moments: (i) the period of the index date, where the baseline information of patients will be collected; (ii) and the follow-up period, during this period the clinical results will be evaluated as well as the continuation of the treatment in the study population and for specific subpopulations.

Those patients who initiated treatment with any oral anticoagulant between January 2013 and June 30, 2018 will be included. This means that patients who start warfarin and NOACs would

be included within this period. Patients who initiate NOACs within the established period and who have been exposed to warfarin before 2013 will also be included.

Only the exposure period will be considered with the initial treatment, even in those patients who were on warfarin treatment before 2013, in the latter, the follow-up will be the treatment initiation with a NOAC in case of change after 2013. Follow-up will be carried out until the patient has a switch of treatment, discontinuation, death, first stroke/ systemic embolism, or major bleeding, or until end of follow-up, June 30, 2019 (Figure 2).

Figure 2. Inclusion of Patients

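### With no event window separate from the back-dated discontinuation date, a stroke or major bleed after the last fill with no refill may be censored rather than counted

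*Combined protocol and SAP*

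**What the plan says.** Section 7.3.1 defines persistence as time on the anticoagulant, "calculated as the time in days from the index date to the date of discontinuation or change to treatment". Discontinuation arises in two ways. One is a change of drug: "discontinuation will be defined as a change of treatment, that is, to another OAC". The other is a refill gap, which is described twice with different starting points: "when there is no evidence of a prescription for 60 days from the last supply delivered", and failure to receive the next prescription "within 60 days after the end of the previous prescription". For the gap route, "the date of the last prescription will be considered as the final date of persistence". No such dating sentence is written for the change route.

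Section 7.1 sets the window: "Follow-up will be carried out until the patient has a switch of treatment, discontinuation, death, first stroke/ systemic embolism, or major bleeding", or 30 June 2019. It adds that "Only the exposure period will be considered with the initial treatment". Section 7.2 gives a similar list, without death. The definitions of major bleeding and ischemic stroke in 7.3.1 count diagnoses only within follow-up and give no lag or grace days. Those of hemorrhagic stroke and systemic embolism state no window. The exploratory objective in section 6 is "To descriptively assess the time to clinical events (Effectiveness and Safety Outcomes) among patients persistent on OAC therapy".

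The text before the switch and persistence definitions, and one item in the censoring list of 7.7, are redacted.

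**The concern.** Persistence runs to the date of discontinuation, and for the gap route its final date is the last prescription, so the two dates coincide. If that date also closes follow-up, whether an event is counted depends on what happens after it. A bleed that leads the patient to stop the drug for good always lies after the last fill. The same bleed in a patient who refills lies inside follow-up.

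Kaplan-Meier estimation assumes that censoring carries no information about the event. Here the event itself would bring on the censoring and place it at an earlier date. The stroke/systemic embolism and major-bleeding curves would both be too low. The plan compares no treatments, so the absolute incidence is itself the result, and the bias passes straight into what is published.

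**Working it through.** The plan gives no event rate or expected event count, so there is no figure to reproduce. The check has two parts.

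**1. Tracing the dates.** Assume a 30-day supply, a last fill on day 300 and a major bleed on day 312.

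- *The index drug is never refilled.* The gap is met on day 360 (60 days from delivery) or day 390 (supply ends on day 330, plus 60). Either way persistence ends on day 300. Taking the earliest listed end of follow-up, the bleed comes 312 − 300 = 12 days too late and the patient is censored event-free.
- *The index drug is refilled within the gap.* There is no discontinuation, and the bleed is counted.
- *The patient changes to another anticoagulant on day 320.* Discontinuation is the change on day 320, and the bleed is inside follow-up. (Exclusion g in 7.2.2, on exposure to more than one anticoagulant, may remove such a patient for a different reason.)

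**2. Size under the literal reading.** Let q be the share of first events after which the index drug is never refilled, d the yearly rate of stopping for unrelated reasons, and s the days between fills. The share of events kept is about

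K = (1 − q) × (1 − d × (s/2)/365.25).

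The first factor removes events that themselves end refilling. The second removes events followed by an unrelated stop before the next fill, an average wait of s/2 days. None of q, d and s is in the documents; all are assumptions. With d = 0.5 and s = 30, the second factor is 1 − 0.5 × 15/365.25 = 0.979.

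A simulation used exponential event and stopping times, 30-day fills, at most two years of follow-up and an assumed true rate of 3 per 100 patient-years. Scaled from 400,000 patients to the plan's 7,500, it had about 277 true events. Ending follow-up at the last fill gave:

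| q | K from formula | Events counted | Rate per 100 patient-years |
|---|---|---|---|
| 0.2 | 78% | 216 | 2.38 |
| 0.4 | 59% | 161 | 1.78 |
| 0.6 | 39% | 107 | 1.18 |
| 0.8 | 20% | 55 | 0.60 |

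At q = 0.5, with 30- or 90-day fills and d of 0.3 to 0.8, 46% to 50% of events were kept.

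With longer windows in the same simulation:

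- To the end of the last supply: 282 to 284 events.
- To 60 days after the last delivery: 293 to 295.
- To 60 days after the end of supply: 304 to 306.

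The rate was about 3.0 in all three cases. The additional events come with their own person-time. The agreement also depends on the simulation holding the event rate the same before and after stopping, which need not be true of anticoagulated patients.

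**The case against.** A reader might infer that follow-up certainly stops at the last fill, that treatment-ending events are never counted, and that fatal events are selectively lost. The documents do not support that much.

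- The back-dating sentence defines the end of persistence. No sentence makes it the censoring date for clinical outcomes.
- Section 7.1 lists stroke/systemic embolism and major bleeding as ends of follow-up in their own right. On day 312 the gap has not yet elapsed, so the bleed can be read as closing follow-up that day. Section 7.3.1 also places persistence inside the patient's follow-up and censors it when follow-up ends.
- The abstract studies time to discontinuation and change of treatment among patients without an event, and 7.7 repeats this with a redaction. That suggests event status is settled first.
- Section 7.1 lists death separately, so a fatal event need not pass through the refill-gap rule.
- Treatment ended by a change to another anticoagulant is not back-dated.
- The redacted text could contain a clarifying rule.
- The simulation builds in the literal reading and largely returns the q put into it. It illustrates size and is not evidence of how the analysis will be run.

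All of this stands, but it does not settle the matter. Being event-free presupposes a window, so the event-free analysis cannot define one. Persistence is measured within follow-up while follow-up ends at discontinuation, which is circular without an order of precedence. Even if the event takes precedence, the plan does not say how long after the last fill it may occur.

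**Conclusion.** The plan sets neither a censoring date for clinical events nor a rule for an event that falls between the last fill and the 60-day gap. Applied literally, its date rules may censor strokes and major bleeds that are not followed by another fill of the index drug, and they bias incidence downwards. An event-first reading is possible but unstated, so two analysts could follow the plan and report different rates.

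The size cannot be derived from the documents. Under the literal reading the loss is roughly q, so assumed shares of 10% to 75% lose about 10% to 75% of events. Events ended by a change of drug are outside the problem, and deaths may be. The conclusion rests on the visible text only. Severity is moderate: the affected outcomes are exploratory and descriptive, and the primary objectives do not depend on this event window.

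**What to change.** In 7.1 and 7.7, define the censoring date for clinical events separately from the end date of persistence:

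- Count first stroke/systemic embolism and first major bleed from the index date to the earliest of switch, death, 30 June 2019 or, without a refill, the day the 60-day no-supply gap is met.
- State that an event inside that window takes precedence over a back-dated discontinuation.
- Reconcile the two starting points of the 60-day rule in 7.3.1, since they close the window on different days.
- Add a sensitivity analysis that counts events only to the end of the last supply.

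The cost is a few sentences and a recalculated censoring date. Fill and event dates are already in Table 1. End of supply is already needed for the version of the gap rule that starts there. The visible part of Table 1 lists prescription date, dose and frequency but no days supplied, so confirm that this can be derived. The downside is that some off-drug days and events in the gap are counted as on treatment; the sensitivity analysis shows how much this matters. The change affects the analysis only.
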